**Table 6 Example of Washout Periods**

Treatment	Washout period
Leflunomide	12 weeks*
Abatacept	8 weeks
Adalimumab	8 weeks
Certolizumab	8 weeks
Infliximab	8 weeks
Golimumab	8 weeks
Tocilizumab	8 weeks
Hydroxychloroquine	8 weeks
Tofacitinib	8 weeks
Etanercept	4 weeks
Anakinra	4 weeks
Sulfasalazine	4 weeks
Azathioprine	4 weeks

\* At least 12 weeks or a minimum of 4 weeks prior to the beginning of Part A if after 11 days of standard cholestyramine washout.

## **5 REPORTING OF ADVERSE EVENTS**

### **5.1 Adverse Event (AE)**

An AE is defined as “any untoward medical occurrence in a patient or clinical investigation patient administered a pharmaceutical product and which does not necessarily have to have a causal relationship with this treatment.”

An AE can therefore be any unfavorable and unintended sign (including an abnormal laboratory finding, for example), symptom, or disease temporally associated with the use of a medicinal product, whether or not considered related to the medicinal product.

### **5.2 Serious Adverse Events (SAE)**

A SAE is any untoward medical occurrence that:

- results in death;
- is life-threatening. The term “life-threatening event” refers to an event in which the patient was at risk of death at the time of the event; it does not refer to an event which hypothetically might have caused death if it were more severe;
- requires inpatient hospitalization or prolongation of existing hospitalization: Hospital admissions and/or surgical operations planned before or during a study are not considered AEs if the illness or disease existed before the subject was enrolled in the study, provided that it did not deteriorate in an unexpected way during the study. Hospitalizations required purely for the purposes of performing study procedures are not SAEs;
- results in persistent or significant disability/incapacity;
- is a congenital anomaly/birth defect, which includes ectopic pregnancy, spontaneous abortion, intrauterine fetal demise, or neonatal death. In addition, infant death after 1 month should be reported as a SAE when the investigator assesses the infant death as related or possibly related to exposure to investigational product;
- any other medically or scientifically significant event that, although it may not be immediately life-threatening or result in death or hospitalization, endangers the patient or requires that appropriate measures be taken to avoid any of the events listed above (e.g., bronchospasm requiring intensive treatment, blood dyscrasia or convulsion not requiring hospitalization, drug dependency or abuse).

### **5.3 Adverse Drug Reactions**

An adverse drug reaction (ADR) is defined as a noxious and unintended response to a medicinal product related to any dose.

AEs which meet all of the following criteria:

- Serious
- Unexpected (i.e. is not consistent with the currently applicable Investigator Brochure list of AEs)
- There is at least a reasonable possibility that there is a causal relationship between the event and the medicinal product

will be classified as Suspected Unexpected Serious Adverse Reactions (SUSARs) and should be reported to the relevant ethics committee and to the relevant Health Authorities for expedited reporting in accordance with Directive 2001/20/EC or as per national regulatory requirements in participating countries.

### **5.4 Adverse Event of Special Interest (AESI)**

An AE of special interest (AESI) is one of scientific and medical interest specific to understanding of the study drug and may require close monitoring and rapid communication by the Investigator to the Sponsor and/or QuintilesIMS. An AESI may be serious or non-serious. The rapid reporting of AESIs allows ongoing surveillance of these events in order to characterize and understand them in association with the use of this study drug. All AESIs must be reported in an expedited manner similar to SAEs (i.e., non-serious AESIs also must follow serious timelines).

The following will be considered AESIs in this study: PML, hepatitis reactivation, mucocutaneous reactions, infusion reactions, anaphylactic reactions, and serious infections.

#### **5.4.1 Progressive Multifocal Leukoencephalopathy**

The Investigator is required to monitor the patients throughout the study for any new or worsening neurological symptoms or signs that may be suggestive of PML. Typical symptoms are diverse, and include cognitive or visual disorders, hemiparesis, confusion, and behavioral disorders. If a patient develops new or worsening neurological signs or symptoms, he/she will be evaluated for PML. Neurological warning signs include:

- Major changes in vision, unusual eye movements.
- Loss of balance or coordination.

- Disorientation or confusion.

If PML is suspected, further dosing must be suspended until PML has been excluded.

Consultation with a neurologist should be considered as clinically indicated. If any doubt exists, further evaluation, including an MRI scan (preferably with contrast), cerebrospinal fluid testing for John Cunningham viral deoxyribonucleic acid (DNA), and repeat neurological assessments, should be considered.

The Sponsor must be notified of any suspected PML cases within 24 hours of awareness according to the procedure outlined in the Site Manual. If any patient reports PML during the study, the patient must be discontinued from study treatment and followed up until resolution at the discretion of the Investigator.

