	
 
To prevent missing data in important supportive efficacy and safety analysis, patients who discontinued study treatment, will also attend all visits until week 52.
 
Patients, Investigators, joint assessor and other study personnel (except pharmacist) will remain blinded to the treatments throughout the entire Treatment Period (52 weeks).
 
An interim analysis of 10 patients per arm (30 patients in total) of safety data collected up to Week 4 and 20 patients per arm (60 patients in total) of safety data collected upto Week 12 are planned.
 
The study will be unblinded at Week 24 and an interim CSR will be prepared based on the 24-week data of all patients. The investigators and patients will remain blinded to treatment assignment during the post Week 24 follow-up period.
 
An independent Data Safety Monitoring Board (DSMB) will be assigned for this study. The DSMB will review available study data at pre-specified time points as outlined in the DSMB charter.
 
Investigators will be instructed to monitor the patients throughout the study to detect the first symptoms or neurological signs suggestive of progressive multifocal leukoencephalopathy (PML, i.e., cognitive or visual disorders, hemiparesis, confusion or behavior disorders). If the patients develop new neurological signs or symptoms they should be evaluated for PML. Neurological warning signs include: major changes in vision, unusual eye movements; loss of balance or coordination; and disorientation or confusion. Any patient who is suspected of developing PML will be discontinued from the study treatment and the AE will be followed closely, at the discretion of the Investigator.
 
	
Number of patients:	Approximately 282 patients will be randomized into the study, at approximately 70 investigative centers.	

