**Figure 1 Study Design**

Standard arthritis assessments and safety assessments will be performed. A disease activity score based on a 28 joint count (DAS28) will be calculated by the study personnel at regularly scheduled visits. At least one experienced, independent joint assessor, blinded to other study assessments as well as the dosing regimen, will be identified at each study center to perform the swollen and tender joint counts.

A provision is made for patients to initiate “rescue therapy” with the use of one non-biologic DMARD after Week 16 of the study (see Section 3.2.6).

Patients with rheumatoid arthritis (<50% improvement from Baseline in both the swollen and tender joint counts) who have been followed up during Part A will be provided with

additional treatment of study drug with two 1,000 mg i.v. infusions (at Week 24 and Week 26 [14 days later]). Patients will attend the study center approximately every 12 weeks during Part B. Patient who are not eligible for the second course of study treatment will also attend all visits until week 52.

Patients may return for unscheduled visits if their medical condition requires immediate attention.

To prevent missing data in important supportive efficacy and safety analysis, patients who discontinued study treatment, will also attend all visits until week 52.

The primary safety concerns associated with rituximab are progressive multifocal leukoencephalopathy (PML), anaphylactic reactions, hepatitis reactivation, and severe mucocutaneous reactions. Patients will be monitored carefully for these during the study.

Any patient who is suspected of developing PML, anaphylactic reactions, hepatitis reactivation, and severe mucocutaneous reactions will be discontinued from the study treatment and the AE will be followed closely, at the discretion of the Investigator.

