### **3.7.3 Individual Patient**

If a patient discontinues the study treatment prematurely, the reason given must be fully evaluated and recorded appropriately in the source documents and the patient's eCRF. If the patient is discontinued from study treatment because of an AE, that AE should be indicated as the reason for discontinuation.

The Investigator can discontinue treatment of a patient at any time if medically necessary. In addition, patients meeting the patient discontinuation criteria must be discontinued from the study treatment.

Patients will be discontinued from the study treatment in the following circumstances:

- A patient who does not meet the enrolment criteria is inadvertently randomized, that patient must be discontinued from study treatment and the Sponsor or Clinical Research Organization (CRO) must be contacted.
- The Investigator decides that the patient should be discontinued from study treatment. If this decision is made because of an intolerable AE or a clinically significant laboratory value, the study drug is to be discontinued and appropriate measures are to be taken. The Sponsor or designee is to be notified immediately.
- Patient non-compliance, defined as refusal or inability to adhere to the study schedule or procedures (see Section 3.12).
- Treatment with a prohibited concomitant medication other than the use of appropriate medications for the treatment of AEs under the direction of the Sponsor and/or Investigator or Sub-investigator
- Lack of efficacy. Subjects who lack efficacy can be included in the PK and efficacy analysis. Patients receiving rescue therapy prior to Week 24 would not be eligible for second course of infusion.
- Patients who meet any of the following specific safety discontinuation criteria, however can be included for the PK analysis:
  - Patients who develop severe infusion-related reactions, especially severe dyspnea, bronchospasm or hypoxia, should have the infusion interrupted immediately to receive aggressive symptomatic treatment. In all patients, the infusion should not be restarted on the same day until complete resolution of all symptoms. At this time, the infusion may be initially resumed at the discretion of the Investigator at not more than one-half the previous rate. If the same ADRs occur for a second time, the infusion should be permanently discontinued.
  - Active TB

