  - Invasive fungal infection or opportunistic infection including, but not limited to, listeriosis, legionellosis or pneumocystis.
  - Hepatitis B virus reactivation, in some cases resulting in fulminant hepatitis, or hepatic failure

- Any other AEs which, in the opinion of the Investigator or the Sponsor, could compromise the patient's safety or well-being if they continue to participate in the study.
- PML. Neurological warning signs include: major changes in vision, unusual eye movements; loss of balance or coordination; and disorientation or confusion
- Cancer: any malignant lesion. Patients with basal cell and squamous cell carcinomas of the skin or carcinoma in situ of the cervix uteri that has been excised and cured, may be continued on the study at the discretion of the Investigator.
- Pregnancy in a female participant
- Patient lost to follow-up despite reasonable efforts to make contact with the patient
- Patients who have a delay of >15 days in receiving the second infusion due to an AE or otherwise
- Judgment by the Investigator or Sub-investigator that study treatment discontinuation is necessary for reasons other than those described above.

To prevent missing data in important supportive efficacy and safety analysis, patients who discontinued study drug, will also attend all visits until week 52.

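### The protocol gives conflicting instructions for suspected PML: the Synopsis and Section 3.1 end study treatment, while Section 5.4.1 only suspends dosing until PML is excluded

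*Protocol*

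**What the plan says.** Four places in the protocol tell a site what to do about PML.

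- **Section 5.4.1** separates two states. On suspicion: "If PML is suspected, further dosing must be suspended until PML has been excluded". On a reported case: "If any patient reports PML during the study, the patient must be discontinued from study treatment".
- **Synopsis, Treatment Regimen**, acts on suspicion: "Any patient who is suspected of developing PML will be discontinued from the study treatment".
- **Section 3.1** (text after Figure 1) does the same, grouping PML with three other risks: "Any patient who is suspected of developing PML, anaphylactic reactions, hepatitis reactivation, and severe mucocutaneous reactions will be discontinued from the study treatment".
- **Section 3.7.3** states that "patients meeting the patient discontinuation criteria must be discontinued from the study treatment", and its list of safety criteria includes "PML. Neurological warning signs include: major changes in vision, unusual eye movements; loss of balance or coordination; and disorientation or confusion". It does not say whether the entry means suspected or confirmed disease.

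Discontinuation here refers to study treatment, not to the study. Section 3.7.3 adds that "patients who discontinued study drug, will also attend all visits until week 52". The SAP contains no instruction on PML.

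**The concern.** The trigger is the same in three of the four places, but the action differs. A suspension that lasts until PML is excluded can be lifted. A discontinuation of study treatment has no stated route back. A site that suspects PML, works the patient up and excludes it cannot follow both.

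Section 3.1 names PML first among the primary safety concerns, Section 5.4 makes it an adverse event of special interest, and approximately 70 centres have to apply the rule. The listed warning signs, such as confusion or loss of balance, are not specific to PML, and Table 2 schedules a neurological examination at every visit. Suspicion that is later cleared is therefore plausible, and those are the cases in which the texts diverge.

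The main issue is an ambiguous safety instruction. The secondary issue is statistical: whether a patient receives the second Part A infusion bears on membership of the PK, PD and per-protocol (PP) sets.

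**Working it through.** No figure is involved, so the check is to set the instructions side by side and follow each possible course of events.

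**Inputs**

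- Action on suspicion: Section 5.4.1 against the Synopsis and Section 3.1, as quoted above.
- Infusions: two in Part A (Day 1, Day 15) and, for eligible patients, two in Part B (Weeks 24 and 26).
- Delay of the second infusion: at most 15 days from its scheduled date (Section 3.2.2), so with scheduling on Day 15 no later than Day 15 + 15 = Day 30. A longer delay means discontinuation (Sections 3.2.2 and 3.7.3).
- Analysis sets: the PK and PD sets need both planned Part A doses (SAP 4.6, 4.7). The PP set needs both Part A infusions and continued study assessments to Week 24 (SAP 4.5).

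**Scenarios**

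| Course of events | Section 5.4.1 | Synopsis and Section 3.1 | Do they differ? |
|---|---|---|---|
| PML confirmed | Treatment ends | Treatment ends | No |
| Suspicion after the patient's last infusion | No infusion left to suspend | No infusion left to stop | Not in dosing |
| Suspicion between Day 1 and Day 15 infusions, not excluded within the 15-day delay | Suspended, then discontinued under the delay rule | Treatment ends | Not in the outcome |
| Same, but excluded within the delay | Second Part A infusion can still be given | Second Part A infusion not given | **Yes**: dosing, and PK, PD and PP membership |
| Suspicion after both Part A infusions, excluded before Week 24, patient otherwise eligible for the second course | Second course possible | No second course | **Yes**: Part B dosing only |
| Suspicion between the Week 24 and Week 26 infusions, excluded in time | Week 26 infusion possible | Week 26 infusion not given | **Yes**: Part B dosing only |

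**Reading the table**

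1. The instructions diverge only when two conditions hold together: PML is later excluded, and an infusion is still due.
2. Within that group, SAP set membership can change only in the fourth row, because all three sets are tied to the Part A infusions. A patient discontinued later keeps attending visits, so the SAP's PP condition on assessments can still be met.
3. Even in the fourth row, inclusion is possible rather than assured. The PK and PD sets also exclude major deviations or events thought to affect PK or PD, and the PP set allows exclusion for situations affecting efficacy assessments.
4. In the fifth row, for a patient in the Rituxan arm, the instruction also decides whether that patient enters the 1:1 re-randomisation (Section 3.2.3).
5. Disposition counts can move as well, since the SAP (Section 8) counts a patient as completing Part A only if study treatment was not discontinued.
6. Section 3.7.3 does not settle the matter. If its PML entry covers suspicion, it sides with the Synopsis and Section 3.1. If it covers only confirmed disease, it is compatible with Section 5.4.1. The listing of warning signs beside the diagnosis leaves both readings open.

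**The case against.** **The texts may describe two stages.** The Synopsis first has new neurological signs evaluated for PML and only then turns to the patient suspected of it. Section 5.4.1 could be taken to cover the work-up, and the Synopsis and Section 3.1 the suspicion that remains afterwards. This does not hold, because Section 5.4.1 uses the same word, suspected, for the state in which dosing is only held.

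**Discontinued may mean paused.** Section 5.4.5 does speak of rituximab being discontinued temporarily or permanently after infusion reactions, but there the qualifier is explicit. The Synopsis and Section 3.1 have none. Section 3.2.1 contrasts a temporary interruption with discontinuation of study treatment, and Section 3.7.3 treats discontinuation as an end point with a recorded reason.

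**The reach is narrow.** This objection stands. A reader might infer that every suspected case is handled differently, or that one text lets dosing continue under suspicion. The documents support neither. All three instructions that address suspicion stop dosing at once, and confirmed disease ends treatment on any reading. A reader might also infer that PK and PP membership is generally at risk. Under the SAP it is not: only the interval between the two Part A infusions matters, and only if the suspicion is cleared in time. The protocol's own PP definition (Section 6.2.1.4) refers to continuing study treatment up to Week 24 and could be read more widely, but SAP 4.5 replaces that with continued assessments.

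**Conclusion.** The contradiction is real. It sits in a stated safety rule and cannot be put down to missing detail or a misprint. On the same trigger, two places end study treatment and a third holds it pending exclusion; a fourth does not define its trigger; nothing ranks them or provides for a restart.

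Its effect is limited to patients in whom PML is suspected, then excluded, with an infusion still due. For them it decides whether the remaining Part A infusion or the second course may be given. For the SAP's PK, PD and PP sets it matters only between the Day 1 and Day 15 infusions, with exclusion inside the 15-day delay. How many patients that would be cannot be derived from the documents. I expect few: against the planned minimum of 84 evaluable patients per group, one patient is 1/84, or about 1.2%. The study's conclusions are unlikely to turn on this; the reason to correct it is clarity of the safety instruction.

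Two assumptions: that a reported case in Section 5.4.1 means a diagnosed one, and that discontinuation of study treatment is permanent unless the text says otherwise.

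**What to change.** Reconcile the Synopsis, Section 3.1, Section 3.7.3 and Section 5.4.1 so that they give:

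- one instruction for suspected PML, stating whether study treatment may resume once PML is excluded;
- one instruction for confirmed PML;
- in Section 3.7.3, a statement of which of the two states its PML criterion refers to.

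Which clinical rule applies is for the sponsor to decide; this point takes no position on it. The revised text should also say whether a cleared suspicion is recorded as an interruption or as a treatment discontinuation, so that the disposition tables and analysis sets follow from it.

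The cost is protocol wording and a notice to sites. No new data, design change or sample-size change is needed. If dosing is already complete, the study report should list any patient in whom PML was suspected and state which instruction was applied.

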#### **5.4.2 Hepatitis Reactivation**

If a patient develops reactivation of HBV while on rituximab, the patient should be managed as outlined in Section 3.2.7.

#### **5.4.3 Serious Infections**

Serious infections are defined as infections requiring i.v. antibiotics or meeting the definition of an SAE.

#### **5.4.4 Mucocutaneous Reactions**

Mucocutaneous reactions, some with fatal outcome, can occur in patients treated with rituximab. These reactions include paraneoplastic pemphigus, Stevens-Johnson syndrome, lichenoid dermatitis, vesiculobullous dermatitis, and toxic epidermal necrolysis. The onset of these reactions has been variable and includes reports with onset on the first day of rituximab exposure. Rituximab should be discontinued in patients who experience a severe mucocutaneous reaction. The safety of re-administration of rituximab to patients with severe mucocutaneous reactions has not been determined.

#### **5.4.5 Infusion Reactions**

An acute onset infusion reaction generally occurs within 24 hours of infusion of the study drug. Rituximab can cause severe, including fatal, infusion reactions. Severe reactions typically occur during the first infusion with time to onset of 30 to 120 minutes. Rituximab-induced infusion reactions and sequelae include urticaria, hypotension, angioedema, hypoxia, bronchospasm, pulmonary infiltrates, acute respiratory distress syndrome,

myocardial infarction, ventricular fibrillation, cardiogenic shock, anaphylactoid events, or death.

Medical management (e.g., glucocorticoids, epinephrine, bronchodilators, or oxygen) for infusion reactions must be instituted as needed. Depending on the severity of the infusion reaction and the required interventions, rituximab may be temporarily or permanently discontinued. Resume infusion at a minimum 50% reduction in rate after symptoms have resolved. Closely monitor patients with pre-existing cardiac or pulmonary conditions.

Infusion reactions should be reported in the eCRF as AEs, or SAEs if it meets the seriousness criteria, with the event term “infusion-related reaction”. The signs and symptoms of the infusion reaction should be described in the appropriate part of the eCRF. Please refer also to Section 5.4.6 (Anaphylaxis).

